8.1.2. Relationship Categorization

A physician/investigator must make the assessment of relationship between the IP and each AE. The PI should decide whether, in their medical judgment, there is a reasonable possibility that the event may have been caused by the IP. If there is no valid reason for suggesting a relationship, the AE should be classified as "not related." If a relationship between the AE and the investigational product is at least reasonably possible (i.e. the relationship cannot be ruled out) the AE should be considered "related." The causality assessment must be documented in the source document.

The following additional guidance may be helpful:

Term	Relationship definition
Related	The temporal relationship between the event and the administration of the IP is compelling and/or follows a known or suspected response pattern to that product, and the event cannot be explained by the subject's medical condition, other therapies, or accident.
Not related	The event can be readily explained by other factors, such as the subject's underlying medical condition, concomitant therapy, or accident, and no plausible temporal or biologic relationship exists between the IP and the event.

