8.2.7. Regulatory Agency, Institutional Review Board, Ethics Committee, and Site Reporting

The sponsor is responsible for notifying the relevant regulatory authorities in the United States (US) and the CRO is responsible for notifying the relevant regulatory authorities in rest of world of related, unexpected SAEs.

In addition, the sponsor or the CRO is responsible for notifying active sites and central institutional review boards (IRBs) of all related, unexpected SAEs occurring during all interventional studies across the GNX program.

The PI is responsible for notifying the local IRBs, local ethics committee, or the relevant local regulatory authority of all SAEs that occur at their site as required.

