- TEAE by SOC, PT, and Severity
- Study drug related TEAEs by SOC, PT
- SAEs by SOC and PT
- TEAEs leading to study drug discontinuation by SOC and PT
- TEAEs leading to dose reduction by SOC and PT
- Adverse events of special interest (AESI)

All AE tables will be sorted by SOC and PT in decreasing frequency of the number of subjects in the GNX group, in the DB summaries and the combined groups in the OL summaries; in case of tied frequencies, the sorting will be alphabetical.

Adverse event listing will identify serious AEs, AE leading to study drug discontinuation, AEs leading to dose reduction, AEs of special interest, and subjects who died during the study.

For purposes of determining treatment emergence, missing start dates will be imputed as shown in Table 3; however, the actual dates, not the imputed ones, will be displayed in the data listing.

Table 3: Handling of Partial or Missing Adverse Event Dates

Partial Missing Start or Stop Date	Imputed Start Date	Imputed Stop Date
Missing month, day, and year	First dose date	
Missing month and day, and the year is present	First dose date if the year is the same as the year of first dose date, else first dose date of the OL if the year is the same as the year of the first OL dose date, else January 1 of the AE start year.	December 31 of that year
Missing day, but year and month are present	First dose date if the year and month are the same as the year and month of first dose date, else first dose date of the OL if the year and month are the same as the year and month of the first OL dose date, else the 1 st of the AE start month.	Last day of that month
Missing month, but year and day are present	Assume day is also missing and impute as above	Missing month imputed as December

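### Protocol 8.1.2 gives two different tests for a drug-related adverse event, and events with a plausible drug link and another possible cause fit neither row of its table

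*Protocol*

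**What the plan says.** Protocol 8.1.2 asks the investigator to judge whether "there is a reasonable possibility that the event may have been caused by the IP". Two instructions follow. For the negative: "If there is no valid reason for suggesting a relationship, the AE should be classified as" *not related*. For the positive, the category *related* applies "If a relationship between the AE and the investigational product is at least reasonably possible (i.e. the relationship cannot be ruled out".

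A two-row table then follows, introduced as additional guidance that may help, with its second column headed as the definition of the relationship.

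- **Related:** the timing relative to "administration of the IP is compelling and/or follows a known or suspected response pattern to that product, and the event cannot be explained"; the competing causes named are the underlying condition, other treatment and accident.
- **Not related:** other factors readily account for the event, and there is no plausible temporal or biological link to the product.

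The result is used in three places.

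- **Notification:** under Protocol 8.2.7 regulators are told of related, unexpected SAEs, and the sponsor or CRO is responsible for "notifying active sites and central institutional review boards (IRBs) of all related, unexpected SAEs".
- **Post-study reporting:** Protocol 8.2.4 requires SAEs found after study completion to be reported only if they are considered related.
- **Analysis:** Protocol 9.14 and SAP 9.1 present AEs judged related by the investigator, including "Study drug related TEAEs by SOC, PT". SAP 9.1 recognises two levels only and gives no definition of its own.

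**The concern.** The text sets a low bar: a reasonable possibility is enough. The table sets a high one: even when the event "is compelling and/or follows a known or suspected response pattern to that product", it also has to be free of any other explanation. The table's rows are not complements either, so an event can fail both.

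The conflict matters in this population. Subjects have a seizure disorder, and study drug is added to their standard anti-seizure treatment (Protocol 3.1), so another explanation will often be available. Protocol 2.1 gives an example from the earlier open-label study: four SAEs in PCDH19 subjects were possibly related to study drug, three of them related to seizures. Read literally, the table could keep seizure events of that kind out of *Related*, because the underlying epilepsy could explain them.

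If sites differ in which test they apply, the same clinical event can be counted as drug-related at one site and not at another. It can also trigger notification at one and not the other.

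**Working it through.** No sample size, power or event figure is involved, and the plan states no number to reproduce. The check is a comparison of the two rules.

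**Inputs.** Both rules come from Protocol 8.1.2. The two-level scale comes from SAP 9.1.

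**Step 1: set up the cases.** Cross the strength of the link to study drug (none; plausible only; compelling timing or known/suspected pattern) with whether another explanation is readily available (no; yes). This gives 3 × 2 = 6 cases. A plausible link is taken to meet the text's test of reasonable possibility.

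**Step 2: classify each case under each rule.**

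| Link to study drug | Other explanation | Text | Table |
|---|---|---|---|
| None | No | Not related | Neither row |
| None | Yes | Not related | Not related |
| Plausible only | No | Related | Neither row |
| Plausible only | Yes | Related | Neither row |
| Compelling or known pattern | No | Related | Related |
| Compelling or known pattern | Yes | Related | Neither row |

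**Step 3: count.**

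- Text: 4 related + 2 not related = 6, so every case is classified.
- Table: 1 related + 1 not related = 2, so 6 − 2 = 4 cases are undefined.
- Of the 4 cases the text calls related, the table calls 1 related and leaves 4 − 1 = 3 undefined. It puts none of the four in its *Not related* row.

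These are logical cases, not expected event frequencies.

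**Step 4: sensitivity of the tables.** The synopsis expects approximately 25 randomised subjects, 1:1, so about 12 or 13 per arm. One subject moving in or out of a related-TEAE row changes that arm's percentage by 1/13 = 7.7 to 1/12 = 8.3 points, about 8. This shows how much one inconsistent call weighs. It does not estimate how many there will be.

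**The case against.** The best reply is that the text governs. It is directive, while the table is offered only as help. The text's two halves already cover nearly everything, and an investigator whose event fits neither row can go back to the text and record *related*. The summary of changes shows that the July 2019 amendment deliberately put the cannot-be-ruled-out wording into 8.1.2, so the inclusive test is evidently intended. Much of this stands and lowers the severity. It does not remove the defect: no section says which prevails, and the table's column heading presents its rows as definitions.

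The safety net is also real. All SAEs, whatever the attribution, go to the sponsor's safety department and the medical monitor within 24 hours (Protocol 8.2.2, 8.2.4). Investigators notify local boards or authorities of all SAEs at their site as required (8.2.7). A monitoring committee has ongoing access to safety data (9.4). SAP 9.1 tabulates all TEAEs by treatment group regardless of attribution, so the comparison with placebo does not rest on causality calls.

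A reader might infer three stronger things that the documents do not support.

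- **That the table classes plausibly related events as *Not related*.** It does not, because that row requires that no plausible link exists. Such events could end up there only because the scale has two levels and they have failed the *Related* row.
- **That the effect can be sized from the fragile X trial in Protocol 1.2.** Somnolence there was 33.9% on ganaxolone and 5.6% on placebo, a difference of 33.9 − 5.6 = 28.3 points. That is a difference in incidence in another population and says nothing about misclassification here.
- **That every CNS event has a competing explanation in the background antiepileptic drugs.** Protocol 5.2.1 requires stable regimens through the double-blind phase, although it also allows reduction or discontinuation when medically warranted. New somnolence during titration is not automatically explained by an unchanged drug. Protocol 8.1.4 also keeps seizures within normal fluctuation out of the AE data.

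**Conclusion.** Protocol 8.1.2 is wrong as written, as an internal inconsistency: two thresholds for one binary judgment, with no rule of precedence. Three of the four logical cases that the text calls related have no home in the table.

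The practical size is unknown. It depends on how many investigators work from the table and how often another cause is available, and the documents give neither. Site training material and eCRF instructions, which might settle the matter in practice, are not part of the documents. The exposure is confined to the drug-related TEAE tables, notification of related unexpected SAEs and post-study SAE reporting. Routine SAE reporting to the sponsor during the study and the all-TEAE comparison are not affected. This is worth correcting, but it does not threaten the trial's main safety conclusions.

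**What to change.** Choose one of two changes to Protocol 8.1.2:

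1. Rewrite the two table rows so that *Related* means a reasonable possibility that cannot be ruled out, and *Not related* is everything else. Every AE then falls in exactly one category.
2. Delete the table and state that the text governs.

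Either is a change to a protocol definition, so it needs an amendment with sponsor and IRB/EC approval (Protocol 10.3.2) and notification of sites. The amendment should also say whether AEs already assessed will be re-reviewed. Without that, events before and after the change would be judged by different standards. Any re-review of double-blind AEs should be finished before those data are unblinded. SAP 9.1 needs no change, since it takes its categories from the protocol.

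The cost is a small amendment burden, some re-review if chosen, and possibly a higher count of related AEs. Enrollment has stopped, but the note to Protocol Table 2 anticipates approximately 3 more years of open-label treatment, so the correction would still apply to future events.

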8.1.3. Outcome Categorization

The outcome of AEs must be recorded during the course of the study on the eCRF. Outcomes are as follows:

- Fatal
- Not recovered/not resolved
- Recovered/resolved
- Recovered/resolved with sequelae
- Recovering/resolving
- Unknown

8.1.4. Symptoms of the Disease Under Study

Symptoms of the disease under study should not be classified as AEs as long as they are within the normal day-to-day fluctuation or expected progression of the disease and are part of the efficacy data to be collected in the study; however, significant worsening of the symptoms should be recorded as an AE.

8.1.5. Clinical Laboratory and Other Safety Evaluations

A change in the value of a clinical laboratory, vital sign, ECG assessment can represent an AE if the change is clinically significant or if, during treatment with the IP, a shift of a parameter is observed from a normal value to an abnormal value, or there is a further worsening of an already abnormal value. When evaluating such changes, the extent of deviation from the reference range, the duration until return to the reference range (either while continuing treatment or after the end of treatment with the IP), and the range of variation of the respective parameter within its reference range must be taken into consideration.

If, at the end of the treatment phase, there are abnormal clinical laboratory, vital sign, or ECG values that were not present in the pretreatment findings observed closest to the start of study treatment, further investigations should be performed until the values return to within the reference range or until a plausible explanation (eg, concomitant disease) is found for the abnormal values.

The PI should decide, based on the above criteria and the clinical condition of a subject, whether a change in a clinical laboratory, vital sign, or ECG parameter is clinically significant and therefore represents an AE.

8.1.6. Pregnancy

All pregnancies are to be reported from the time informed consent (and subject assent) is signed until the defined follow-up period.

Any report of pregnancy for any study subject must be reported within 24 hours to the Marinus Safety Department or its delegate using the Pregnancy Report Form. A copy of the Pregnancy Report Form (and any applicable follow-up reports) must also be sent to the CRO/Marinus medical monitor using the details specified in the emergency contact information section at the beginning of the protocol. The pregnant study subject must be withdrawn from the study.

Every effort should be made to gather information regarding the pregnancy outcome and condition of the infant. It is the responsibility of the PI to obtain this information within 30 calendar days after the initial notification and approximately 30 calendar days after delivery.

Pregnancy complications such as spontaneous abortion/miscarriage or congenital abnormality are considered SAEs and must be reported as outlined in Section 8.2.2 of the protocol using the Marinus Clinical Study Serious Adverse Event Form. Non-serious AEs are to be reported as per clinical eCRF guidelines. Note: An elective abortion is not considered an SAE.

In addition to the above, if the PI determines that the pregnancy meets serious criteria, it must be reported as an SAE to the Marinus Safety Department or delegate as outlined in Section 8.2.2 of the protocol using the Marinus Clinical Study Serious Adverse Event Form. The test date of the first positive serum/urine β -human chorionic gonadotropin test or ultrasound result will determine the pregnancy onset date.

8.1.7. Abuse, Misuse, Overdose, and Medication Error

Abuse, misuse, overdose, or medication error must be reported to the sponsor per the SAE reporting procedure whether or not it results in an AE/SAE as described in Section 8.2.2. Note: The 24-hour reporting requirement for SAEs does not apply to reports of abuse, misuse, overdose, or medication errors unless these result in an SAE.

The categories below are not mutually exclusive; the event can meet more than 1 category.

- **Abuse:** Persistent or sporadic intentional intake of an IP for a nonmedical purpose (eg, to alter one's state of consciousness or get high) in a manner that may be detrimental to the individual and/or society.
- **Misuse:** Intentional use of an IP other than as directed or indicated at any dose. (Note: This includes a situation in which the IP is not used as directed at the dose prescribed by the protocol.)
- **Overdose:** Intentional or unintentional intake of a dose of an IP exceeding a prespecified total daily dose of the product.
- **Medication error:** An error made in prescribing, dispensing, administering, and/or use of an IP. Medication errors are reportable to the sponsor only as defined below.
 - Cases of subjects missing doses of the IP are not considered reportable.
 - Applicable only for the IP under investigation.
 - The administration and/or use of an expired IP should be considered as a reportable medication error.
 - All IP provided to pediatric subjects should be supervised by the parent/caregiver/LAR. Lapses in supervision should be reported.

8.2. Serious Adverse Event Procedures

8.2.1. Reference Safety Information

The reference for safety information for this study is the GNX Investigator's Brochure, which the sponsor has provided under separate cover to all PIs.

8.2.2. Reporting Procedures

All initial and follow-up SAE reports must be reported by the PI to the Marinus Safety Department or its delegate *and* the CRO/Marinus medical monitor within 24 hours of the first awareness of the event. Note: The 24-hour reporting requirement for SAEs does not apply to reports of abuse, misuse, overdose, or medication errors unless they result in an SAE.

The PI must complete, sign, and date the Marinus Clinical Study Serious Adverse Event Form and verify the accuracy of the information recorded on the form with the corresponding source documents (Note: Source documents are not to be sent unless requested) and fax or e-mail the form to the Marinus Safety Department or its delegate. A copy of the Marinus Clinical Study Serious Adverse Event Form (and any applicable follow-up reports) must also be sent to the CRO/Marinus medical monitor using the details specified in the emergency contact information section of the protocol.

8.2.3. Serious Adverse Event Definition

An SAE is any untoward medical occurrence (whether considered to be related to IP or not) that at any dose:

- Results in death
- Is life-threatening. Note: The term “life-threatening” in the definition of “serious” refers to an event in which the subject was at risk of death at the time of the event; it does not refer to an event that hypothetically might have caused death if it were more severe.
- Requires inpatient hospitalization or prolongation of existing hospitalization. Note: Hospitalizations, which are the result of elective or previously scheduled surgery for preexisting conditions that have not worsened after initiation of treatment, should not be classified as SAEs. For example, an admission for a previously scheduled ventral hernia repair would not be classified as an SAE; however, a complication resulting from a hospitalization for an elective or previously scheduled surgery that meets serious criteria must be reported as an SAE.
- Results in persistent or significant disability or incapacity
- Is a congenital abnormality or birth defect
- Is an important medical event. Note: Important medical events that may not result in death, be life-threatening, or require hospitalization may be considered an SAEs when, based on appropriate medical judgment, they jeopardize the subject and may require medical or surgical intervention to prevent one of the outcomes listed in this definition. Examples of such medical events include allergic bronchospasm requiring intensive treatment in an emergency room or at home; blood dyscrasias or convulsions that do not result in inpatient hospitalization; or the development of drug dependency or drug abuse.

8.2.4. Serious Adverse Event Collection Time Frame

All SAEs (regardless of relationship to study) are collected from the time the parent/caregiver/LAR/subject signs the informed consent/assent until the defined follow-up period stated and must be reported to the Marinus Safety Department *and* the CRO/Marinus medical monitor within 24 hours of the first awareness of the event.

In addition, any SAE considered “related” to the IP and discovered by the PI at any interval after the study has completed must be reported to the Marinus Safety Department within 24 hours of the first awareness of the event.

8.2.5. Serious Adverse Event Onset and Resolution Dates

The onset date of the SAE is defined as the date the event meets serious criteria. The resolution date is the date the event no longer meets serious criteria, the date the symptoms resolve, or the date the event is considered chronic. In the case of hospitalizations, the hospital admission and discharge dates are considered the onset and resolution dates, respectively.

In addition, any signs or symptoms experienced by the subject after signing the informed consent form (and subject assent) or leading up to the onset date of the SAE, or following the resolution date of the SAE, must be recorded as an AE, if appropriate.

8.2.6. Fatal Outcome

Any SAE that results in the subject's death (i.e., the SAE was noted as the primary cause of death) must have fatal checked as an outcome, with the date of death recorded as the resolution date. For all other events ongoing at the time of death that did not contribute to the subject's death, the outcome should be considered not resolved, without a resolution date recorded.

For any SAE that results in the subject's death or any ongoing events at the time of death, unless another IP action was previously taken (eg, the drug was interrupted, reduced, or withdrawn), the action taken with the IP should be recorded as "dose not changed" or "not applicable" (if the subject never received the IP). The IP action of "withdrawn" should not be selected solely as a result of the subject's death.

8.2.7. Regulatory Agency, Institutional Review Board, Ethics Committee, and Site Reporting

The sponsor is responsible for notifying the relevant regulatory authorities in the United States (US) and the CRO is responsible for notifying the relevant regulatory authorities in rest of world of related, unexpected SAEs.

In addition, the sponsor or the CRO is responsible for notifying active sites and central institutional review boards (IRBs) of all related, unexpected SAEs occurring during all interventional studies across the GNX program.

The PI is responsible for notifying the local IRBs, local ethics committee, or the relevant local regulatory authority of all SAEs that occur at their site as required.

8.3. Adverse Events of Special Interest

8.3.1. Reference Safety Information

The following represent the Adverse Events of Special Interest:

- Rash
- Adverse Events that would be classified under reproductive system and breast disorders system organ class

9. DATA MANAGEMENT AND STATISTICAL METHODS

9.1. Data Collection

The PI's authorized site personnel must enter the information required by the protocol on the eCRF. A study monitor will visit each site in accordance with the monitoring plan and review the eCRF data against the source data for completeness and accuracy. Discrepancies between source data and data entered on the eCRF will be addressed by qualified site personnel. When a data discrepancy warrants correction, the correction will be made by authorized site personnel. Data collection procedures will be discussed with the site at the site initiation visit and/or at the PI's meeting. Once a subject is screened, it is expected that site personnel will complete the eCRF entry within approximately 7 business days of the subject's visit.

The subject's parent/caregiver/LAR must enter the information required by the protocol in the eDiary. A study monitor will review all seizure diary entries in accordance with the monitoring plan for completeness and accuracy. Discrepancies will be addressed by the subjects' parent/caregiver/LAR and qualified site personnel. When a data discrepancy warrants correction, the correction will be made by the subjects' parent/caregiver/LAR and authorized site personnel. Data collection procedures will be discussed with the site at the site initiation visit and/or at the investigator's meeting. Once the subject's parent/caregiver/LAR signs informed consent (and subject assent), it is expected that all eDiary entries will be made daily. Retrospective entry of diary events (seizure and medication) can be completed by the caregiver up to 5 days later and proxy entry by the site is also available to the site staff (greater than 5 days), but neither method is encouraged.

Telephone Follow-up visits are allowed to be conducted via secure email per institutional policy if granted by individual sites IRB/EC.

